12.9 Analysis Convention for Composite Endpoints

The value of composite endpoints, such as deep remission, is decided by the value of each component at the visits with planned measurements for all components. In details, taking deep remission as an example, one of its components, clinical remission, is measured every eight weeks, i.e., Week 0, 8, 16, 24 etc. The other component, CDEIS remission, is measured every year, i.e., Week 0, Week 48, Week 104, Week 152, Week 200. Hence the observed value of deep remission will be evaluated at Week 0, Week 48, Week 104,

Week 152, Week 200 based on the value of each component endpoint at the corresponding visit, according to [Table 11](#) below, where, for deep remission, the endpoint A = Clinical remission, the endpoint B = CDEIS remission.

Table 11. How to calculate the observed value of endpoint C = A and B for different scenarios

Scenarios	A at Week X*	B at Week X*	C at Week X*
Scenario 1	1	1	1
Scenario 2/3/4	1/0/0	0/1/0	0/0/0
Scenario 5/6	1/Missing	Missing/1	Missing/Missing
Scenario 7/8	0/Missing	Missing/0	0
Scenario 9	Missing	Missing	Missing

* X = The visits with both measurements A and B planned. It will be 0, 48, 104, 152, 200 for deep remission.

The other endpoints which have multiple components, i.e., "A and B and C...," such as "Proportion of subjects with average daily SF ≤ 2.8 and not worse than baseline and average daily AP score ≤ 1 and not worse than baseline," could follow the similar logic.

For endpoints with the structure of "A or B," such as "Proportion of subjects with $\geq 60\%$ decrease in average daily SF and/or $\geq 35\%$ decrease in average daily AP score and both not worse than baseline, and/or achievement of average daily SF ≤ 2.8 and AP ≤ 1 and both not worse than baseline," the observed value of such endpoint "C = A or B" can be determined following the logic displayed in [Table 12](#) below.

Table 12. How to calculate the observed value of endpoint C = A or B for different scenarios.

Scenarios	A at Week X*	B at Week X*	C at Week X*
Scenario 1	0	0	0
Scenario 2/3/4	1/0/1	1/1/0	1/1/1
Scenario 5/6	1/Missing	Missing/1	1/1
Scenario 7/8	0/Missing	Missing/0	Missing/Missing
Scenario 9	Missing	Missing	Missing

* X = The visits with both measurements A and B planned.

Document Approval

Study M15989 - Statistical Analysis Plan Version 1 - 15Jul2019 (E3 16.1.9)

Version: 1.0

Date: 17-Jul-2019 03:46:15 AM

Company ID: 07172019-00F9F6842AA885-00001-en

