10. Every effort should be made for the patient to perform a final ileocolonoscopy at the study visit where the last dose of study medication is administered. For patients with early EoT, every effort should be made to perform a final ileocolonoscopy within 2 weeks following the early EoT visit.
11. Colonoscopy is not to be repeated if done at preceding visit.
12. IBDQ should be completed before site staff interaction and study drug administration.
13. Blood samples for PK and ADA will be drawn BEFORE drug administration, i.e. pre-dose, whenever visits coincide.
14. Visit 1.1 is applicable only for those patients that had visit E1 more than 5 days before Visit 1. Visit 1.1 can be performed by phone, fax or email.
15. IRT has to be called only once at V1 or V1.1 after assessment if s.c or i.v. re-induction is needed.
16. In case patient had visit E1 less than 5 days before Visit 1, CDAI assessment and new patient diary dispense should be done at Visit 1.

**FLOW CHART 2: PATIENTS (1) ROLLING-OVER AT WEEK 52 FROM PRECEDING TRIAL 1311.6
(WITH CLINICAL RESPONSE OR REMISSION AT VISIT E5) VISITS 1-18**

Trial Period	Screening														Treatment period						
	1 ^{1,2}	1.1 ^{1,4}	2	3	4	5	6	7	8	9	10	11	12	13	14	15	16	17	18		
Visit	0	1	6	14	22	30	38	46	54	62	70	78	86	94	102	110	118	126	134		
Week	+5	+5	±7	±7	±7	±7	±7	±7	±7	±7	±7	±7	±7	±7	±7	±7	±7	±7	±7		
Time window (days)																					
Informed consent	X																				
Assessment of eligibility	X																				
LABS/SAFETY ASSESSMENTS																					
Detailed physical examination	X																				
Targeted physical examination (incl. vital signs)		X	X	X	X	X	X	X	X	X	X	X	X	X	X	X	X	X	X	X	
Weight	X	X	X	X	X	X	X	X	X	X	X	X	X	X	X	X	X	X	X	X	
12 Lead Resting-ECG	X																				
Urine Pregnancy test ⁴	X		X	X	X	X	X	X	X	X	X	X	X	X	X	X	X	X	X	X	
Laboratory tests (serum chemistry, hematology, urinalysis) ⁹	X		X	X	X	X	X	X	X	X	X	X	X	X	X	X	X	X	X	X	
QuantiFERON-TB Gold In-Tube test ⁵	X																				

Trial Period	Screening							Treatment period											
	1 ^{1,2}	1,1 ¹⁴	2	3	4	5	6	7	8	9	10	11	12	13	14	15	16	17	18
Visit	0	1	6	14	22	30	38	46	54	62	70	78	86	94	102	110	118	126	134
Week																			
Time window (days)	+5	+5	±7	±7	±7	±7	±7	±7	±7	±7	±7	±7	±7	±7	±7	±7	±7	±7	±7
EFFICACY																			
ASSESSMENTS																			
Dispense patient diary for screening ¹⁴	X																		
Crohn's Disease Activity Index (CDAI), PRO-2	X ¹⁵	X	X	X	X	X	X	X	X	X	X	X	X	X	X	X	X	X	X

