6.4 Definition of Visit Windows

Since subjects do not always adhere to the study visit schedule, the following rules will be applied to assign actual visits to protocol-specified visits including early termination visits. For each study visit mentioned in the protocol, a nominal or target day will be selected to represent the corresponding visit along with a window around the target day. Windows will be selected in a non-overlapping fashion so that a date collected on the case

report form (CRF) does not correspond to multiple visit windows. Moreover, windows will not discard any post-baseline measurement recorded on the CRF. If a subject had 2 or more actual visits in one visit window, the visit closest to the target will be used as the study visit for that window. If two visits are equidistant from the target day, then the later visit will be used for reporting.

The visit windows and the target/nominal day for each study visit are shown in the tables below. The visit windows defined below will be based on relative days to either first dose on IV or first dose on SC.

Table 1. Windows for subcutaneous injection period for ITT_SC (SA_SC) population, using for Vital sign, Lab Values, Fistula exam, CDAI, Review patient diary (PRO data).

Nominal Visit Week^d	Lower Bound	Nominal Day	Upper Bound
0	-999	1 ^a	1
8	2	57	85
X ^c	$1 + 7*(X - 4) + 1$	$1 + 7*X$	$1 + 7*(X + 4)$
200	1374	1401	9999 ^b

- a. Day of first dose of study drug for subcutaneous injection.
- b. It is minimum of (the last dose date + 140 days, the first dose date of Study M16-000 sub-Study 3) for the subjects who entered the Study M16-000 sub-Study 3; otherwise it is the last dose date +140 days.
- c. $X = 8*i$, $i = 2, \dots, 24$.
- d. Nominal visit week is a transformation of the protocol-specified week. For the patients' schedule following the Flow Chart 1, nominal visit week = protocol-specified week – 4. For the patients' schedule following the Flow Chart 2, nominal visit week = protocol-specified week – 6. For the patients' schedule following the Flow Chart 3 (only for subcutaneous injection period), nominal visit week = protocol-specified week – 16.

Table 2. Windows for subcutaneous injection period for ITT_SC population, using for CDEIS and SES-CD.

Nominal Visit Week ^c	Lower Bound	Nominal Day	Upper Bound
0	-999	1 ^a	1
48	2	337	533
104	534	729	897
152	898	1065	1233
200	1234	1401	9999 ^b

- a. Day of first dose of study drug for subcutaneous injection.

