9.0 Efficacy Analysis

9.1 General Considerations

There is no formal statistical hypothesis test planned. Descriptive analyses will be used to analyze the proportion of participants achieving the efficacy endpoints. The study is designed to gain extensive documentation of safety and efficacy.

9.1.1 Analysis of Efficacy Endpoints by Variable Type**9.1.2 Missing Data Imputation for Efficacy Endpoints**

Missing data imputation will be done only for categorical efficacy variables. For the analysis other than efficacy, no imputation will be done for missing values.

Non-Responder Imputation (NRI)

The NRI approach is used for binary efficacy variables. These variables can take values of 'Achieved' or 'Not Achieved' or may be missing for any reason including discontinuation from study. According to the NRI imputation approach, all missing values will be considered as 'Not Achieved.' If a subject has missing value for a specific visit, the data will be imputed using NRI only for the period which the visit belongs to.

Observed Case (OC)

Observed case analysis will be performed, i.e., missing values will not be imputed. An analysis using only the observed data will be performed as a sensitivity analysis for primary and secondary efficacy endpoints.

Imputation of Missing Dates

For baseline, efficacy, and safety parameters, if the day and/or month are missing, the following conventions will be used to impute the missing dates:

- 01 for missing start day
- End of month for missing end day
- January 1st for missing start month
- December 31st for missing end month

In case of partially missing AE start and stop dates, the dates will be imputed by comparing to first dose date of study medication so that the corresponding AEs will be made treatment-emergent whenever possible. If the start date of an AE is partially

missing and the month is the same as the start date of a new therapy, the AE will be made treatment emergent to the new therapy.

In case of missing or partially missing study drug dosing dates, the dates will not be imputed. Subjects will be treated as not receiving dose on that date.

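### Deep remission (SAP 12.9): when the colonoscopy used at a week falls before that week's CDAI window, Table 11 keeps endoscopic failures as 0 and makes successes Missing, so observed-case inclusion depends on the endoscopic result

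*SAP*

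**What the plan says.** **Pairing.** SAP 12.9 takes each component's value at the same nominal week: "Hence the observed value of deep remission will be evaluated at Week 0, Week 48, Week 104", followed by Weeks 152 and 200. It has no rule that pairs by date or by visit.

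**Windows (SAP 6.4).** Table 1 is headed "Windows for subcutaneous injection period for ITT_SC (SA_SC) population, using for Vital sign, Lab Values, Fistula exam, CDAI, Review patient diary" and has 8-week windows. Table 2 is headed "Windows for subcutaneous injection period for ITT_SC population, using for CDEIS and SES-CD" and has roughly annual windows. The rules are meant to "assign actual visits to protocol-specified visits including early termination visits", so off-schedule final visits pass through both tables. With several visits in one window, "the visit closest to the target will be used as the study visit for that window".

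**Table 11 (SAP 12.9).** With CDAI remission missing, deep remission is 0 if CDEIS remission is 0 (scenario 8) and Missing if CDEIS remission is 1 (scenario 6).

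**Analyses.** SAP 9.1.2 says of OC: "An analysis using only the observed data will be performed as a sensitivity analysis for primary and secondary efficacy endpoints". NRI turns every missing value into Not Achieved. SAP 9.3 reports both for the secondary endpoints.

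**Timing of the final colonoscopy.** Protocol Flow Chart 1, footnote 10, asks sites to "perform a final ileocolonoscopy at the study visit where the last dose of study medication is administered". For patients who stop early, "every effort should be made to perform a final ileocolonoscopy within 2 weeks following the early EoT visit". Footnote 3 then plans only a telephone call 140 days after the last dose.

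**The concern.** The final colonoscopy follows the end of treatment, not the annual schedule, so final CDAI and CDEIS pairs can fall on any study day. The same-week rule works only if both values get the same week label, and over long stretches of follow-up they do not. A CDAI that was recorded then counts as missing for the composite, and Table 11 resolves that gap differently for endoscopic failures and successes.

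What is at stake is the OC rate of deep remission. It is meant as a check on NRI, but in these patients it drops endoscopic successes and keeps failures. NRI counts the same dropped patients as Not Achieved, including those in CDAI remission at the colonoscopy visit. If both rates are lowered together, their agreement reassures wrongly.

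**Working it through.** **Step 1. Reproduce the printed windows.** The Table 1 window for Week X runs from day 1 + 7(X − 4) + 1 to day 1 + 7(X + 4). The Table 2 upper bounds are midpoints of the nominal days: (337 + 729)/2 = 533, (729 + 1065)/2 = 897 and (1065 + 1401)/2 = 1233. The Week 200 lower bound in Table 1 is 1 + 7 × 196 + 1 = 1374. All agree with the SAP.

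| Week | CDAI days (Table 1) | CDEIS days (Table 2) | Same-visit pair with CDAI in an earlier week (early split) | Number of days |
|---|---|---|---|---|
| 48 | 310–365 | 2–533 | 2–309 | 308 |
| 104 | 702–757 | 534–897 | 534–701 | 168 |
| 152 | 1038–1093 | 898–1233 | 898–1037 | 140 |
| 200 | from 1374 | from 1234 | 1234–1373 | 140 |

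Over days 2 to 1373 (1,372 days), 756 are early splits, 448 are late splits (CDAI in a later week than CDEIS) and 168 are aligned. If the colonoscopy follows the early EoT visit by 14 days, the early-split ranges end at days 323, 715, 1051 and 1387.

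**Step 2. Which splits matter.**
- Early split with no later CDAI in the matching window: component A is missing, so B = 0 gives 0 and B = 1 gives Missing.
- Late split: if the scheduled colonoscopy was done on time, it is closer to target and replaces the final one. If it was missed but the Week X CDAI was done, the final CDEIS is paired with an older CDAI. The result is not missing in either case.

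**Step 3. Direction.** Let the OC rate be D/M. Restoring k dropped endoscopic remitters, of whom a share a′ is in CDAI remission, gives (D + k·a′)/(M + k). This exceeds D/M only if a′ > D/M.

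**Step 4. Size, by illustration.** The documents give no EoT dates. Assume that the final colonoscopy is uniform over days 400–1373 (974 days), scheduled annual visits are attended, CDAI remission is a = 0.8, CDEIS remission is c = 0.3 to 0.7, and the two are independent. With all pairs kept the rate is a·c. Under the SAP,

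OC = a·c·other / (other + (1 − c)·split),

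where split counts early-split days and other counts days that give an aligned Week X pair.

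For c = 0.5 and the same visit:
- Week 104: split 168, other 672 (days 702–1373). OC = 0.4 × 672/(672 + 84) = 268.8/756 = 35.6%, against 40.0%.
- Week 152: split 140, other 336 (days 1038–1373). OC = 0.4 × 336/(336 + 70) = 134.4/406 = 33.1%, against 40.0%.

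| Timing of last CDAI | Week 104 shortfall, c = 0.3–0.7 | Week 152 shortfall, c = 0.3–0.7 |
|---|---|---|
| 14 days before colonoscopy | 3.9–4.9 points | 6.0–7.7 points |
| Same visit | 3.6–4.4 | 5.4–6.9 |
| Further EoT CDAI 56 days later (interval assumed) | 2.3–2.9 | 3.1–3.9 |

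**Step 5. Sensitivity to a′ (c = 0.5, same visit).** At a′ = 0.5, Week 104 becomes (268.8 + 84 × 0.5)/840 = 37.0%, a shortfall of 1.4 points. Week 152 becomes (134.4 + 70 × 0.5)/476 = 35.6%, a shortfall of 2.5. The shortfall is zero at a′ = 35.6% and 33.1%.

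**Step 6. Precision.** With 60 patients the OC denominators are 60 × 756/974 = 47 and 60 × 406/974 = 25. The standard errors are √(0.24/47) = 7 points and √(0.24/25) = 10 points.

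**Step 7. NRI in the same case.** The Week 104 rate is 268.8/974 = 27.6%, against 0.4 × 840/974 = 34.5% if the recorded pairs are used. At Week 152 it is 134.4/974 = 13.8%, against 0.4 × 476/974 = 19.5%.

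**Step 8. Week 200.** If no contributing patient has a CDAI from day 1374 on, every observed value there is 0. OC deep remission is then 0% by construction, whatever the patients' state.

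**The case against.** The strongest reply is that Table 11 is ordinary AND logic. One known failure settles the composite and one known success does not; Table 12 applies the matching OR logic. Each retained 0 is correct for that patient. This stands. The fault lies in who enters the OC denominator, and it arises here from values that were recorded but labelled with another week.

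Several stronger readings are tempting, and the documents do not support them:
- *Every split pair is affected.* Late splits are not when the Week X CDAI was done, and they are 448 of the 1,204 split days.
- *OC drops only endoscopic successes.* Scenarios 5 and 9 also drop CDAI remitters without a colonoscopy and patients missing both components.
- *OC is always too low.* Step 3 shows that the direction can reverse.
- *The windows are the only source of the 0/Missing pattern.* It also arises at scheduled visits when CDAI cannot be scored (SAP 12.1), and in mirror form when the colonoscopy is missing. With the values of Step 4 (c = 0.5) and an assumed 20% of colonoscopies missing, OC is 0.32/(0.80 + 0.20 × 0.20) = 38.1% instead of 40.0%.

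A simpler rule would set the composite to Missing whenever either component is missing. Under independence it gives 40.0% in OC. But it discards correct zeros, ignores recorded pairs, and leaves NRI scoring recorded remitters as Not Achieved.

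The effect is also below one standard error, on an untested endpoint. That limits its weight. It does not justify a selection by outcome that can be removed with data already collected.

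**Conclusion.** Wrong as written, with low weight. For early-split pairs with no later CDAI in the matching window, post-baseline OC inclusion depends on the endoscopic result. This follows from Tables 1, 2 and 11 without any assumption.

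The size does rest on assumptions. With the last CDAI at the colonoscopy visit or 14 days before it, the OC shortfall is about 4 to 5 points at Week 104 and 5 to 8 at Week 152. It is smaller if a later EoT CDAI falls in the window or if CDAI remission among the dropped patients is lower. It reverses if that remission is below the reported OC rate. How many patients are affected depends on EoT dates that the documents do not give. Week 0 is untouched because both windows end on day 1. No error rate is involved, since nothing is tested.

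**What to change.** Add to SAP 12.9: when the CDEIS used at post-baseline Week 48, 104, 152 or 200 has no CDAI in the Table 1 window for that week, component A is the CDAI from the colonoscopy visit, or otherwise the nearest within 14 days. The 14-day limit is a choice to be stated; it equals the protocol's 2-week allowance for the early EoT colonoscopy.

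Derive this once as the observed value of deep remission. OC and NRI then use the same value, and NRI imputes only what is still missing. An OC-only fill would make one patient-week a success in OC and Not Achieved in NRI. Leave Week 0 and the stand-alone CDAI and CDEIS tables unchanged, and footnote that such pairs carry the Table 2 week label.

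The cost is a few sentences, a footnote and a small derivation, with no new data. In the illustration with a 14-day lag, every split pair is recovered and OC returns to a·c, which is 40.0% at c = 0.5.

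The downsides should be stated:
- The label can precede its target by up to 335, 195, 167 and 167 days at Weeks 48, 104, 152 and 200, as it already can for stand-alone CDEIS.
- The borrowed CDAI is tabulated at another week in the clinical remission table.
- Some patients who ended treatment early can count as achieved in NRI at the labelled week, as they already can for stand-alone CDEIS. SAP 12.2 has a sentence in the PRO-2 appendix that scores patients who discontinue before an endpoint as not achieved, so 12.9 should say which rule governs deep remission.
- The 0/Missing asymmetry remains where a component is truly missing.
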